3.4.1.3 Injection Site Reactions

For assessing the safety and reactogenicity of HB-101, the incidence and severity of localized or generalized injection site reactions will be summarized by symptom type and by injection site and symptom type for the Safety Population.

3.4.1.4 Immunogenicity

To assess the immunogenicity of HB-101, descriptive central statistics will be presented for the following immunogenicity parameters using the Immunogenicity Population:

- CMV neut
- CMV ELISPOT pp65
- CMV ELISPOT gB

The summary will also be based on the number of doses of medication or placebo received (only for 2 and 3 doses). For CMV ELISPOT pp65, CMV ELISPOT gB, and the combination of CMV ELISPOT pp65 and gB, counts and percentages of positive responses will be displayed in addition to the descriptive central statistics. A Wilcoxon signed-rank test will be performed by each treatment and dose group versus the Pre-Dose 1 values from that group. A Mann-Whitney U test of HB-101 versus the corresponding Placebo at each time point will also be performed. The CMV neut parameter will undergo all tests and summaries of the other parameters with the

addition of a 95% confidence interval of the geometric mean titer and a categorical summary of the increase of titer result from Pre-Dose 1 based on the following ranges:

- >2-fold
- >3-fold
- >4-fold

The CMV neut parameter summarization will also be repeated by viremia status (with or without) at Pre-Dose 1 (Group 3 only) and day of transplant.

The result of CMV ELISPOT pp65, CMV ELISPOT gB, pp65 together with gB, and CMV neut result will be plotted against the time of dose received and day of transplant by study medication, dose, and group. The boxplot of CMV neut result by treatment and dose will be provided. The plot of seroconversion rates by dose and treatment will be plotted against the time of dose received and day of transplant. The CMV neutralization antibody titers (NTA) responses and CMV viremia will be plotted by treatment, dose, and viremia status against the time of dose received and day of transplant.

The pre- and post-transplant immunosuppressant use will be summarized by preferred term for all post-transplant randomized patients.

The CMV serology information will be summarized for transplant recipient and kidney donor.

For patients who developed HLA sensitization, the pre- and post-dose sample and recipient genotype information will be listed.

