2.3 Study Endpoints

2.3.1 *Primary Endpoints*

For objective of assessing the safety and reactogenicity of HB-101, the primary endpoints are

- Incidence and severity of Adverse events (AEs), serious adverse events (SAEs), and changes in laboratory values
- Incidence and severity of localized or generalized injection site reactions

For objective of assessing the immunogenicity of HB-101, the primary endpoints are descriptive central statistics of the following immunogenicity parameters:

- CMV Neutralization (neut)
- CMV Enzyme-linked immunospot (ELISPOT) phosphoprotein 65 Kd (pp65)
- CMV ELISPOT gB

2.3.2 *Secondary Efficacy Endpoints*

- Incidence and time to clinically significant CMV infection, CMV disease, and CMV syndrome after transplant
- Incidence and time to CMV viremia requiring anti-viral therapy after transplant
- Incidence and duration (in days) of anti-CMV therapy courses (at therapeutic doses) required after transplant
- Incidence and time to quantifiable CMV DNAemia , peak CMV DNAemia level, and duration of CMV DNAemia above the limit of quantitation after transplant
- Incidence and time to graft failure and organ rejection after transplant

2.3.3 *Exploratory Efficacy Endpoints*

Descriptive central statistics of the following immunogenicity parameters:

- CMV Intracellular cytokine staining (ICS) pp65
- CMV ICS gB
- LCMV ELISPOT nucleoprotein (NP)

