3.1.4 Hypothesis Testing

There is no formal hypothesis testing for this study. This study is for an initial assessment of the safety and immunogenicity of the vaccine candidate.

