3.4 Endpoint Assessment

The mITT Population will be used for all endpoint analyses related to efficacy, the Safety Population for all endpoint analyses related to safety, and the Immunogenicity Population for all endpoint analyses related to immunogenicity. The results of the study will be analyzed descriptively. However, should the results be favorable, subgroup analyses and additional analyses may be performed based on patient characteristics, transplant characteristics, number and timing of vaccinations, or use of immunosuppression to identify factors influencing vaccine response.

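### SAP 3.4.1.4 requires many unlabelled p-values on the primary immunogenicity parameters, but plans no HB-101 versus placebo estimate with an interval and no stated stratification by randomized group

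*SAP*

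**What the plan says.** On the status of the results, SAP 3.1.4 states: "There is no formal hypothesis testing for this study". SAP 3.4 adds: "The results of the study will be analyzed descriptively". SAP 2.3.1 defines the endpoints in the same spirit: "For objective of assessing the immunogenicity of HB-101, the primary endpoints are descriptive central statistics of the following immunogenicity parameters". The three parameters are CMV neut, CMV ELISPOT pp65 and CMV ELISPOT gB.

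On the analysis, SAP 3.4.1.4 says: "A Wilcoxon signed-rank test will be performed by each treatment and dose group versus the Pre-Dose 1 values from that group". It continues: "A Mann-Whitney U test of HB-101 versus the corresponding Placebo at each time point will also be performed". CMV neut goes through the same tests. Summaries are also split by number of doses received, for patients with two and with three doses.

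The immunogenicity table in Appendix A lists eight time points for each parameter: Pre-Dose 1, 2 and 3, Day of Transplant, months 3, 6 and 9 after transplant, and End of Study.

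The planned summaries by arm are the usual descriptive statistics (3.1.3), positive-response rates for the ELISPOT parameters and their combination, and, for neut only, a 95% CI for the geometric mean titer and categories of fold rise (3.4.1.4).

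Groups 1 and 2 are each randomized 2:1 (2.2.2), and results are presented by treatment arm for the two groups together (3.1.3).

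**The concern.** Immunogenicity is a primary objective, and two families of tests are mandatory on its parameters. The SAP gives no significance level, sidedness, main time point or position on multiplicity for them, and does not say in 3.4.1.4 that the p-values are nominal. Whichever visit, parameter or dose stratum falls below 0.05 could therefore be put forward as evidence of immunogenicity.

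The larger gap is estimation. SAP 2.2.4 says the data should help to design and power Phase 3. For immunogenicity, the useful quantity is the size of the HB-101 versus placebo difference and its precision. No such contrast is planned.

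Two details add to this. The between-arm test at each time point includes Pre-Dose 1, before any dosing, where randomized arms differ only by chance. And the Mann-Whitney test is not said to take account of the separate randomization in Groups 1 and 2.

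**Working it through.** The SAP gives no test count, significance level or power, so there is no figure of its own to reproduce.

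**Counting the tests (natural reading)**

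Inputs:
- 3 parameters (2.3.1).
- 2 dose strata (3.4.1.4).
- 3 columns: HB-101 and placebo in Groups 1 and 2 together, and open-label HB-101 in Group 3 (3.1.3).
- 8 time points (Appendix A). Two-dose patients have no Pre-Dose 3 sample, so they have 7. After Pre-Dose 1 this leaves 7 and 6.

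Results:
- Signed-rank: 3 parameters × 3 columns × (7 + 6) = 117.
- Mann-Whitney by dose stratum: 3 × (8 + 7) = 45 with Pre-Dose 1, or 3 × (7 + 6) = 39 without.
- Total: 117 + 45 = 162, or 117 + 39 = 156.

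Other readings:

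| Reading | Signed-rank | Mann-Whitney | Total |
|---|---|---|---|
| Pre-transplant time points only | 45 | 21 | 66 |
| No Group 3, Mann-Whitney not split by dose, no Pre-Dose 1 test | 78 | 21 | 99 |
| Mann-Whitney not split by dose, no Pre-Dose 1 test | 117 | 21 | 138 |
| pp65 and gB combined as a fourth parameter | 156 | 60 | 216 |
| Groups 1 and 2 tested separately | 195 | 90 | 285 |

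**Chance results among the between-arm tests**

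The signed-rank tests on HB-101 should be non-null if the vaccine works, so the between-arm family is the fairer one to use. Assume a two-sided level of 0.05 and no vaccine effect.
- Expected number below 0.05: 39 × 0.05 = 1.95, or 45 × 0.05 = 2.25.
- Probability of at least one if independent: 1 − 0.95^39 = 0.86, or 1 − 0.95^45 = 0.90.
- One common correlation across all 45 tests: about 0.60 at 0.5 and 0.39 at 0.7 (simulated).
- For the 39 tests, correlation between time points only, with parameters and dose strata independent: 0.77 at 0.5 and 0.60 at 0.8 (simulated).

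The expected count does not depend on the correlation. The probability of at least one does.

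**Effect of ignoring the randomized groups**

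The simulation assumed 40 HB-101 and 20 placebo patients in each group, normal outcomes and a nominal two-sided 0.05. The power column assumes a vaccine effect of 0.5 SD. The stratified test is van Elteren.

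| Shift between Groups 1 and 2 | Pooled test, error with no effect | Power, pooled | Power, stratified |
|---|---|---|---|
| 0 | about 5% | 0.71 | 0.71 |
| 0.5 SD | about 4% | 0.68 | 0.70 |
| 1.5 SD | about 1% | 0.50 | 0.71 |

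The 2:1 ratio is the same in both groups, so arm and group are not confounded. The pooled test is conservative and loses power as the groups diverge. With no divergence nothing is lost.

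**The case against.** The strongest reply is that the plan is coherent as it stands. Section 3.1.4 excludes only formal testing, section 3.4 makes the results descriptive, and supplementary p-values in an unpowered Phase 2 study are common. No decision rule in the SAP depends on a p-value. All of this stands. A reader might infer a flat contradiction, or that the p-values have no status at all; the documents support neither. Descriptive status is implied, and what is missing is an explicit label. Lack of a multiplicity adjustment is not itself an error here.

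A reader might also take about 160 as a minimum number of tests. It is not: the signed-rank sentence names no time points, and narrower readings give fewer.

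Nor are the ELISPOT parameters left with p-values alone. Descriptive statistics and response rates by arm are planned for them. What is absent is a contrast between arms with an interval.

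On stratification, it can be said that the word corresponding may mean placebo within the same group, and that Groups 1 and 2 differ by post-transplant management, so a group effect may be small on the Day of Transplant. Both are fair. They limit the likely loss of power, but they leave the wording open on a point that stratifying would settle at little cost.

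The choice of main visit is a judgement. Time since the last dose varies at the Day of Transplant because transplant timing varies.

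**Conclusion.** The point holds in a limited form: minor, or at most a change that should be made. Section 3.4.1.4 orders 156 to 162 tests on the natural reading, without labelling the p-values nominal and without a main comparison. About two chance findings are expected among the 39 to 45 between-arm tests if the vaccine has no effect. That figure rests on an assumed level of 0.05. The probability of at least one ranges from 0.39 to 0.90 over the correlations tried, so it should not be quoted as a single number.

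The more substantial defect is that no HB-101 versus placebo difference with an interval is planned for any primary immunogenicity parameter. The lack of stated stratification is a question of efficiency, not of bias. Its size depends on how far Groups 1 and 2 differ, which the SAP does not tell us, and on the assumed 40:20 split and 0.5 SD effect.

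**What to change.** In 3.4.1.4, add for each primary parameter an HB-101 versus placebo estimate in Groups 1 and 2 with a 95% CI, stratified by randomized group: a geometric mean ratio for CMV neut and a Hodges-Lehmann shift for each ELISPOT parameter. If a p-value is shown beside it, use the van Elteren test.

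State one main time point in advance. Day of Transplant is a reasonable choice because it is the last sample before exposure to the donor kidney. If it is chosen, describe the time since last dose alongside the estimate.

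Drop the between-arm test at Pre-Dose 1. State in 3.1.4 that all p-values in the study are nominal, unadjusted for multiplicity and descriptive.

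The cost is SAP wording and minor reprogramming, which can be done before database lock, when the SAP is to be finalized. The downside is fewer p-values to quote.

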2.2 Study Design

2.2.1 Overview

This is a Phase 2 study of HB-101, a bivalent CMV vaccine, in patients awaiting kidney transplantation and includes a randomized, placebo-controlled portion (Groups 1 and 2) and an open-label portion (Group 3). Approximately 150 patients recruited globally from specified transplant centers will be enrolled. The study will occur at approximately 25 to 40 global sites.

A high-level study schematic of Study H-100-002 is presented in Figure 1.

Figure 1 High-Level Study Schematic

For Groups 1 and 2, adult CMV seronegative (-) patients awaiting kidney transplant from a CMV seropositive (+) living donor will be enrolled according to treatment intent with regard to the method of CMV prevention after transplant (either preemptive or prophylactic) as defined at study enrollment by the investigator and institutional standards.

Patients enrolled into Groups 1 and 2 should have a living donor kidney transplantation ideally planned between 2 to 4 months after the first injection of study drug (HB-101 or placebo).

- Group 1 - The preemptive group will be randomized in a 2:1 ratio (HB-101:placebo) to receive either HB-101 or placebo before transplant. Post-transplant patients will be monitored per preemptive institutional standards.
- Group 2 - The prophylactic group will be randomized in a 2:1 ratio (HB-101:placebo) to receive either HB-101 or placebo before transplant. Post-transplant patients will receive 3 to 6 months of anti-viral prophylaxis following institutional standards.

Enrollment of Group 2 will be limited to no more than 54% of total patients.

For Group 3, adult CMV seropositive (+) patients awaiting kidney transplant from a CMV seropositive (+) or CMV seronegative (-) living donor will be enrolled into Group 3. Post-transplant CMV management will follow either preemptive or prophylactic care as defined at study enrollment by the investigator and institutional standards.

Patients enrolled into Group 3 should have a kidney transplantation from a living donor planned between 2 to 4 months after the first injection of HB-101. Patients in Group 3 will receive HB-101 vaccination(s) prior to their transplant surgery. Enrollment of Group 3 will be a minimum of 15% of total patients.

Patients receiving at least 2 doses of study drug before transplant will be included in the statistical analysis of the efficacy endpoints.

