For groups 1 and 2, adult CMV seronegative (-) patients awaiting kidney transplant from a CMV seropositive (+) living donor will be enrolled into Groups 1 or 2 according to treatment intent with regard to the method of CMV prevention after transplant (either preemptive or prophylactic) as defined at study enrollment by the investigator and institutional standards.

- Group 1 - The preemptive group will be randomized in a 2:1 ratio (HB-101:placebo) to receive either HB-101 or placebo before transplant. Post-transplant patients will be monitored per preemptive institutional standards.
- Group 2 - The prophylactic group will be randomized in a 2:1 ratio (HB-101:placebo) to receive either HB-101 or placebo before transplant. Post-transplant patients will receive 3 to 6 months of anti-viral prophylaxis following institutional standards.

Patients will be randomized via a centralized Interactive Response Technology (IRT) system. Enrollment of Group 2 will be limited to no more than 54% of total patients.

The study is double-blind for Groups 1 and 2; patients and investigators will be blinded to treatment assignment.

Group 3 will be open label. In Group 3, CMV seropositive (+) patients awaiting kidney transplant from a CMV seropositive (+) or CMV seronegative (-) donor will be enrolled to receive HB-101 vaccination(s) prior to their transplant surgery. There will be no randomization or blinding for patients in Group 3. Enrollment of Group 3 will be a minimum of 15% of total patients.

Hookipa Biotech study team members may be unblinded after each patient receives their last dose of study drug and undergoes his/her kidney transplantation. Medpace, the investigator, and study site personnel will remain blinded for the entire study with the exception of the study site pharmacist or designee or research nurse at each site who prepares the study drug for blinded administration.

2.2.3 *Study Drug*

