HB-101 uses replication-deficient lymphocytic choriomeningitis virus (rLCMV) as a vector for a bivalent recombinant vaccine against Human Cytomegalovirus (HCMV). One vector expresses the pp65 protein of HCMV, and one expresses a truncated glycoprotein B (gB) protein of HCMV. The 2 vectors are produced separately. The final drug product is manufactured by mixing 1 batch of rLCMV pp65 and 1 batch of rLCMV gB in a 1:1 ratio based on pp65- and gB-expressing vectors. HB-101 was produced pre-diluted and ready-to-use. HB-101 is formulated at 1.2×10^8 FFU/mL. The product is filled in 2 mL single-dose vials containing 0.7 mL of vaccine. Sodium chloride (0.9% w/v) will be used as the placebo. The sponsor will supply this saline for the study.

2.2.4 *Sample Size Determination*

A total sample size of approximately 150 patients is planned for the study. Patients in Groups 1 and 2 will be randomized with a 2:1 ratio for active versus placebo. Patients in Group 3 will be enrolled to receive open-label HB-101. The sample size has been set for an initial assessment of the safety and immunogenicity of the vaccine candidate, which will provide for approximately 100 patients exposed to the HB-101 vaccine. No formal statistical assessment for sample size determination has been conducted. The sample size is considered adequate to provide the necessary safety and immunogenicity data and help with the determination of point estimates of clinical efficacy endpoints (clinically significant CMV infection as defined by the Food and Drug Administration (FDA) "Guidance for Industry: Cytomegalovirus in Transplantation: Developing Drugs to Treat or Prevent Disease") to design and adequately statistically power Phase 3 trials.

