7. Urine pregnancy test will be limited to patients producing urine daily. CMV = cytomegalovirus; hCG = human chorionic gonadotropin; PCR = polymerase chain reaction; SAE = serious adverse event.

Immunogenicity Analysis and Time Points

	Pre-Dose 1¹	Pre-Dose 2¹ (28 Days After Dose 1²)	Pre-Dose 3¹	Day of Transplant (Prior to Transplant Procedure)	3 Months After Transplant³	6 Months After Transplant³	9 Months After Transplant³	End of Study Visit
Study Assessments								
Study drug injection	X	X	X	-	-	-	-	-
Immunogenicity Testing								
CMV neut	X	X	X	X	X	X	X	X
LCMV neutralizing antibody	X	-	-	X	-	-	-	X
CMV ELISPOT pp65	X	X	X	X	X	X	X	X
CMV ELISPOT gB	X	X	X	X	X	X	X	X
CMV ICS pp65	X	X	X	X	X	X	X	X
CMV ICS gB	X	X	X	X	X	X	X	X
LCMV ELISPOT NP*	X	X	X	X	X	X	X	X

*Possible that analyses will not occur at all time points, e.g., insufficient volumes of blood. 1. Blood collection for immunogenicity will be performed prior to each study drug booster administration. 2. Time (window) from the last dose of study drug (HB-101 or placebo) is 28 days (± 7 days). 3. Time window of follow-up visits after transplant is ± 7 days. CMV = cytomegalovirus; ELISPOT = enzyme-linked immunospot; gB = glycoprotein B; ICS = intracellular cytokine staining; LCMV = lymphocytic choriomeningitis virus; neut = neutralization; NP = nucleoprotein; pp65 = phosphoprotein 65 kD

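### The HB-101 versus placebo test of the primary immunogenicity parameters makes no use of Pre-Dose 1 values, which can cost precision, mainly for ELISPOT (minor)

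*SAP*

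**What the plan says.** SAP Section 3.4.1.4 plans two tests for the primary immunogenicity parameters. Within each arm: "A Wilcoxon signed-rank test will be performed by each treatment and dose group versus the Pre-Dose 1 values from that group". Between arms: "A Mann-Whitney U test of HB-101 versus the corresponding Placebo at each time point will also be performed". For CMV neut it adds a "categorical summary of the increase of titer result from Pre-Dose 1 based on the following ranges" (more than 2-, 3- and 4-fold). The section does not say whether the between-arm test is on actual values or on change. Actual values is the natural reading.

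The immunogenicity table in Appendix A lists Pre-Dose 1 as a sampling point for CMV neut, ELISPOT pp65 and ELISPOT gB, and its footnote says "Blood collection for immunogenicity will be performed prior to each study drug booster administration".

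Placebo exists only in Groups 1 and 2, for which Section 2.2.1 says that "adult CMV seronegative (-) patients awaiting kidney transplant from a CMV seropositive (+) living donor will be enrolled". For the seropositive patients, Section 2.2.2 says "There will be no randomization or blinding for patients in Group 3", so they are outside this comparison. Section 3.1.4 says that the study has no formal hypothesis testing.

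**The concern.** The within-arm test uses the patient's own starting value but has no control. The between-arm test has the control but not the starting value. Only the between-arm test can separate a vaccine response from background, and it concerns primary parameters whose results are meant to inform Phase 3 design (Section 2.2.4).

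Suppose a patient's background reading carries through to later samples. Ignoring it then leaves explainable variation in the comparison, and a chance difference in background between the arms can be read as vaccine effect or can hide one. The covariate is already collected, so using it costs almost nothing.

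**Working it through.** **1. Where Pre-Dose 1 is used.** The signed-rank test uses it within an arm, for all parameters. The fold-rise bands are displayed by arm, for neut only, without a test. The Mann-Whitney test does not use it. So no planned between-arm test uses baseline.

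**2. Arm sizes.** Section 2.2.4: "A total sample size of approximately 150 patients is planned for the study" and "Patients in Groups 1 and 2 will be randomized with a 2:1 ratio for active versus placebo". Group 3 takes at least 15%, so at most 150 × 0.85 = 127.5 patients are randomised: 127.5 × 2/3 = 85 on HB-101 and 127.5 / 3 = 42.5 on placebo, taken as 42.

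**3. Inputs that the SAP does not give.** It states no alpha, effect size, SD, power or baseline correlation for this test, so there is no planned figure to reproduce. Assumed: two-sided 5%, a shift of 0.5 SD, correlation ρ between Pre-Dose 1 and the later value from 0 to 0.7.

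**4. Formula, no values at the assay limit.**

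Power = Φ( 0.5 × √0.955 / (s × √(1/85 + 1/42)) − 1.96 )

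The factor 0.955 is the efficiency of the Mann-Whitney test for normal data. The residual SD s is 1 unadjusted, √(1 − ρ²) with baseline adjustment, and √(2(1 − ρ)) for change scores. Here √(1/85 + 1/42) = √0.03557 = 0.1886, so with s = 1 the first term is 0.5 × 0.9772 / 0.1886 = 2.591 and power is Φ(0.631) = 73.6%. At ρ = 0.5 with adjustment, s = 0.866, the first term is 2.992 and power is Φ(1.032) = 84.9%.

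| ρ | Unadjusted | Adjusted | Change score |
|---|---|---|---|
| 0 | 73.6% | 73.6% | 44.9% |
| 0.3 | 73.6% | 77.5% | 59.1% |
| 0.5 | 73.6% | 84.9% | 73.6% |
| 0.7 | 73.6% | 95.2% | 91.7% |

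Change scores do worse than the planned test below ρ = 0.5.

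**5. Values at the assay limit.** Seronegative patients may have many baselines at the limit, so the gain was simulated at ρ = 0.5 with the same shift and arm sizes, comparing Mann-Whitney with rank ANCOVA (Quade).

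| Share at limit | Limit applied to | Mann-Whitney | Rank ANCOVA | Gain (points) |
|---|---|---|---|---|
| 0% | – | 74.0% | 83.5% | 9.5 |
| 50% | both time points | 67.5% | 77.1% | 9.6 |
| 80% | both time points | 51.2% | 55.9% | 4.7 |
| 90% | baseline only | 73.2% | 76.8% | 3.6 |
| 95% | baseline only | 73.5% | 75.4% | 1.9 |
| 100% | baseline only | 72.9% | 72.9% | 0 |

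The first three rows use 4,000 trials each and the last three 2,000, so each power figure has a standard error of about 0.7 to 1 point. A repeat simulation gave gains of about 8 points at 50%, 4 at 80%, and 1 to 3 at 90 to 95%.

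**6. Validity.** With no treatment effect, the unadjusted test rejected in 4.0% to 5.8% of trials in every scenario, which is 5% within simulation error. Among the tenth of null trials with the largest Pre-Dose 1 imbalance (ρ = 0.5, no limit), it rejected in about 14%, against about 4 to 6% for rank ANCOVA. That is the cost of an unlucky draw, not a fault in the test's overall error rate.

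**7. Smaller dose groups.** With an assumed 42 versus 21 patients, ρ = 0.5 and no limit, power goes from 42.9% to 53.3%. With 43 versus 21 and 90% or 95% of baselines at the limit, the gains are 2.8 points (42.0% to 44.8%) and 1.8 points (42.8% to 44.6%).

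**The case against.** The strongest counter-argument is that there may be little to adjust for. Everyone compared with placebo is CMV seronegative, and the seropositive patients, whose baselines would plausibly vary, have no placebo arm. If nearly all Pre-Dose 1 values are at the limit, the gain is a few points or none. This largely stands for neut. It is weaker for ELISPOT, because serostatus is an antibody criterion and does not fix cellular counts at zero. The SAP gives no baseline distribution for either assay, so neither side can be shown from the document. The planned signed-rank test does not settle it: that test works equally well with every baseline at the limit.

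The SAP also makes no power claim and disclaims formal testing. That limits the severity but does not remove the point, since the tests are planned and their results will be read. Four of the eight sampling points are after transplantation, where the correlation with Pre-Dose 1 may differ, so one value of ρ cannot stand for all of them. The neut fold-rise bands by arm already give an untested view of change against placebo.

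A reader might infer that the planned test is invalid or biased, or that power is certainly lost. The documents support neither. Randomisation protects the error rate, and the loss depends on a correlation that the SAP does not give. Nor does the SAP state that actual values are tested; that is a reading of it.

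**Conclusion.** The point holds as a conditional, minor one. The only randomised comparison of the primary immunogenicity parameters leaves out a covariate that is collected for all of them. At an assumed correlation of 0.5 the power forgone runs from about 10 points with no values at the assay limit, through 8 to 10 at 50% and 4 to 5 at 80%, to about 1 to 3 at 90 to 95% (3.6 in one run with the limit on baselines only). It is zero at no correlation or with all baselines tied. Correlation, effect size and share at the limit are all assumed. The case rests mainly on ELISPOT.

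A reader might also expect adjustment to repair the 2-dose and 3-dose comparisons. It does not: those groups form after randomisation, according to transplant timing, and adjustment for one baseline value does not cure that selection.

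**What to change.** In Section 3.4.1.4:

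- State that the Mann-Whitney test is on actual values.
- For CMV neut, ELISPOT pp65 and ELISPOT gB, at each post-dose time point, add a rank ANCOVA (Quade) of HB-101 versus placebo adjusted for the same parameter's Pre-Dose 1 value: rank the post-dose and the Pre-Dose 1 values over both arms, regress the first ranks on the second, and compare the residuals between arms.
- Keep the unadjusted Mann-Whitney test alongside it.
- Do not use plain change scores in its place, because they lose power when the correlation is below 0.5.

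The cost is a sentence or two of SAP text and a short programming step, with no new samples or visits. Patients without a Pre-Dose 1 sample drop out of the adjusted test, but the retained unadjusted test still includes them. The change should be made before database lock, by which time Section 1 says the SAP will be final.
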